# **Study Protocol and Statistical Analysis Plan**

## **1. Study Background and Rationale**

Microplastics (MPs) are ubiquitous in the environment and have been detected in various foods, making oral ingestion a primary exposure route. MPs may induce gut microbiota dysbiosis, activate inflammation, and interfere with energy metabolism, potentially acting as an environmental risk factor for obesity. Probiotics can restore gut homeostasis and enhance barrier function. The strain *Lactiplantibacillus plantarum* PD01 has shown efficacy in preclinical models in blocking MP translocation and alleviating obesity and inflammation. This study aims to evaluate its efficacy in a human population.

## **2. Study Objectives**

To explore whether probiotic intake can alleviate obesity-related adverse effects caused by microplastic exposure.

## **3. Study Design**

### **3.1 Study Type**

Randomized, double-blind, placebo-controlled intervention trial.

### **3.2 Participants**

**Sample Size:** 96 healthy volunteers.

#### **Inclusion Criteria:**

1. Age 18-65 years.
2. BMI  $\geq 24.0$  kg/m^2 OR central obesity (waist  $\geq 90$ cm men,  $\geq 85$ cm women).

Priority given to those with mild blood lipid/liver function abnormalities.

3. Permanent residents of the local area.
4. Voluntary participation and signed informed consent.

#### **Exclusion Criteria:**

1. Immunodeficiency, severe allergies, or active gastrointestinal diseases.
2. Use of antibiotics, probiotics, or drugs affecting gut function in the past 6 months.

3. Regular use of nutritional supplements in the past 6 months.
4. Smoking or heavy alcohol consumption.
5. Pregnancy or lactation.
6. Weight change >5% in the past 3 months.

### **3.3 Interventions**

**Experimental Group:** Probiotic supplement containing 1.8g Fructooligosaccharides (FOS) + 0.2g *L. plantarum* FABYIO PD01 (10 billion CFU).

**Control Group:** Placebo containing 2.0g Fructooligosaccharides (FOS).

**Dosage:** One pack, three times daily, dissolved in warm water (<40°C), taken with/after meals.

**Duration:** 42 days (6 weeks).

### **3.4 Randomization and Blinding**

**Randomization:** Participants will be stratified by gender and BMI. A computer-generated randomization list (SAS 9.3) will allocate subjects 1:1 to the two groups.

**Blinding:** Double-blind design. Both investigators and participants are blinded to group allocation.

### **3.5 Study Procedures**

Visits occur at Baseline (Week 0), Mid-term (Week 3), and End-point (Week 6).

### **3.6 Outcome Measures**

#### **Primary Outcome Measures:**

1. Fecal microplastics (MPs) levels: Assessed by Py-GC/MS. Includes detection of 11 types of plastics (PC, PE, PP, PS, PA6, PET, PLA, PVC, PA66, PBAT, PMMA). Reported in µg/g dry weight.
2. Gut microbiota composition: Assessed by Fecal Metagenomics sequencing to analyze diversity and functional genes.
3. Blood metabolic profiles: Assessed by untargeted Blood Metabolomics to identify metabolic pathway alterations.
4. Inflammatory cytokines levels: Measurement of serum markers including MCP-1, IL-1β, IL-6, TNF-α, P-selectin, CRP, etc..

5. Blood biochemical indicators: Assessed by automatic biochemical analyzer. Includes liver function and blood lipid indicators (Total Cholesterol, Triglycerides, HDL, LDL).
6. Routine blood examination: Assessed by automatic blood cell analyzer. Includes white blood cell count (WBC) and five-part differential.
7. Anthropometric and body composition indicators: Measurement of body weight, BMI, waist circumference, hip circumference, body fat percentage, and muscle mass via Bioelectrical Impedance Analysis.

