**4. Statistical Analysis Plan**

**Sample Size:** 96 participants.

**Analysis Sets:** Per-Protocol (PP) set and Intention-to-Treat (ITT) set.

**Statistical Methods:** Data will be analyzed using SAS 9.3 software. Continuous variables will be presented as Mean  $\pm$  SD. Repeated measures ANOVA or mixed-effects models will be used to analyze changes in the primary outcome measures (MPs, microbiota, metabolomics, inflammation, biochemistry, blood routine, and InBody data) from baseline to Week 3 and Week 6, comparing the interaction between Group and Time. Significance level is set at  $p < 0.05$ .

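### Fecal microplastics are tested only by a group-by-time interaction; one prespecified, baseline-adjusted arm contrast on the same samples would define the test and usually have more power

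*Combined protocol and SAP*

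**What the plan says.** Section 3.6 lists seven primary outcome groups. The first is "Fecal microplastics (MPs) levels: Assessed by Py-GC/MS", covering 11 polymers and reported in µg/g dry weight. Section 3.5 sets visits at Week 0 (baseline), Week 3 (labelled mid-term) and Week 6 (labelled end-point).

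Section 4 states: "Repeated measures ANOVA or mixed-effects models will be used to analyze changes in the primary outcome measures". Microplastics are named in that list, and the analysis runs "from baseline to Week 3 and Week 6, comparing the interaction between Group and Time". Each participant therefore has one baseline and two on-treatment microplastic values. The interaction is the only comparison named. Nothing says whether baseline is a response or a covariate, or which week or combination of weeks carries the conclusion.

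The size is "96 healthy volunteers" (Section 3.2), and the randomization list "will allocate subjects 1:1 to the two groups" (Section 3.4). Section 4 fixes the level at p < 0.05. The documents give no effect size, SD, visit correlation, target power, dropout rate or stool-collection method.

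**The concern.** The group-by-time interaction can mean two tests here, and neither is aimed at the question of whether the arms differ on treatment.

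- **All three visits as responses.** The interaction has 2 df. It compares the arms on change from baseline, so the baseline value is subtracted at full weight however weakly it predicts later values. The second degree of freedom goes on the shape of the time course.
- **Change scores at Weeks 3 and 6 as responses.** The wording about changes from baseline allows this. The interaction then has 1 df and tests only whether the arm difference moves between Week 3 and Week 6. A benefit present by Week 3 and held to Week 6 would be missed except by chance.

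Fecal microplastic level is the only direct measure of microplastics in the trial, and the total is fixed at 96. An inefficient or ambiguous test on this outcome could leave a real effect undetected. If the choice between models is made after the data are seen, the result is also open to challenge.

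**Working it through.** **Plan's own figure.** The only figure is N = 96. It cannot be reproduced, because no effect, SD or power is given.

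**Inputs.** From the documents: n = 48 per arm (96/2), α = 0.05 (taken as two-sided), visits at Weeks 0, 3 and 6. Assumed: arm difference d = 0.5 SD at Weeks 3 and 6; the same correlation ρ between any two visits, 0.1 to 0.7 in the table; no dropout; no multiplicity adjustment.

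**Formulas.** Power comes from the noncentral F distribution with noncentrality λ; n/2 = 24.

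- 2-df interaction: λ = (n/2) Σ(δₜ − δ̄)² / (1 − ρ), where δ₀ = 0. With equal effects this is (n/2)d²(2/3)/(1 − ρ).
- Week 6, baseline as covariate: λ = (n/2)δ₆² / (1 − ρ²).
- Mean of Weeks 3 and 6, baseline as covariate: λ = (n/2)[(δ₃ + δ₆)/2]² / [(1 + ρ)/2 − ρ²].
- Interaction on the two change scores: λ = (n/2)(δ₆ − δ₃)² / [2(1 − ρ)].

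**At ρ = 0.3, equal effects** (24 × 0.25 = 6):

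- Interaction: 6 × (2/3)/0.7 = 5.71 on 2 df, 55% power.
- Week 6: 6/0.91 = 6.59 on 1 df, 72%.
- Mean: 6/0.56 = 10.71 on 1 df, 90%.
- Interaction on change scores: λ = 0, so power equals the false-positive rate, 5%.

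A simulation of 8,000 trials gave 55.3% for the 2-df interaction and 89.3% for the adjusted mean.

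**Across correlation and time course** (Week 6 effect 0.5 SD):

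| Week 3 effect | ρ | 2-df interaction | Week 6, adjusted | Mean, adjusted |
|---|---|---|---|---|
| 0.5 SD | 0.1 | 45% | 68% | 91% |
| 0.5 SD | 0.3 | 55% | 72% | 90% |
| 0.5 SD | 0.5 | 71% | 80% | 93% |
| 0.5 SD | 0.7 | 91% | 92% | 98% |
| 0.25 SD | 0.3 | 44% | 72% | 68% |
| none | 0.3 | 55% | 72% | 37% |

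**Source of the gain.** The mean change from baseline, without baseline as a covariate, has variance factor (1 + ρ)/2 + 1 − 2ρ = 1.05 at ρ = 0.3. So λ = 6/1.05 = 5.71, the same as the interaction, and power is 66% on 1 df. Moving from 2 df to 1 df takes 55% to 66%; using baseline as a covariate instead of subtracting it takes 66% to 90%. Under equal effects, the ratio of λ for the adjusted mean to λ for the interaction is 3/(1 + 2ρ), so the gain shrinks as correlation rises.

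**When the mean beats Week 6.** Let k be the Week 3 effect as a fraction of the Week 6 effect. The two λ are equal when (1 + k)/2 = √(0.56/0.91) = 0.784, so k is about 0.57 at ρ = 0.3.

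**Baseline-constrained mixed model.** If the arms share one baseline mean, the 2-df joint test of the Week 3 and Week 6 differences has, with equal effects, the same λ as the adjusted mean. At ρ = 0.3 that is 10.71 on 2 df, about 84%.

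**Other inputs, equal effects (interaction, then adjusted mean).** d = 0.4, ρ = 0.1: 30%, 75%. At d = 0.5, ρ = 0.3: with 43 per arm, 51%, 87%; with 41 per arm, 49%, 85%; at α = 0.05/7, 28%, 70%.

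**The case against.** The strongest objection is that Section 4 leaves the model open, so the 55% belongs to one reading. This stands. A mixed model with a common baseline mean is also a group-by-time model, and its 2-df test has about 84% power at correlation 0.3 with equal effects. The adjusted mean then gains about 6 points (90% against 84%), and Week 6 alone, at 72%, would have less power than that joint test. But the plan does not commit to this model, and the wording equally permits the reading with 5% power.

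A second objection is that the mean of Weeks 3 and 6 can do harm. This also stands. With no Week 3 effect at correlation 0.3, it has 37% against 55% for the interaction. The documents give no expected time course, and Section 3.5 labels Week 6 the end-point. So the mean should not be the automatic choice.

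A third is that there is no single microplastic variable to put in the contrast: 11 polymers are listed, with no total and no transformation. That is correct, and the contrast needs a named summary before it can be run. It is equally true of the interaction.

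Three stronger readings are tempting but not supported:

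- A reader might infer that each visit rests on one noisy spot stool. Section 3.6 gives the assay, polymers and units, but not the number of stools, the collection method or within-person variability.
- A reader might take a rise from 55% to 90% as a property of this trial. It holds only for the assumed inputs; at correlation 0.7 the same comparison is 91% to 98%.
- A reader might credit averaging alone. Averaged change scores reach only 66%.

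**Conclusion.** The concern holds as a defect of specification with a likely loss of power. Section 4 names an interaction, does not say which form, and states no baseline adjustment. Under the ordinary three-visit form, a baseline-adjusted Week 6 contrast matches or beats it, to within 0.3 percentage points, at every correlation from 0.1 to 0.8 in all three time courses checked. The advantage is about 17 points at correlation 0.3 with equal effects (72% against 55%), but only about 1 point at correlation 0.7. The adjusted mean does better still when the effect is early and sustained, and worse when it is delayed.

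All power figures rest on an assumed 0.5 SD effect, equal visit correlations, full follow-up and an unadjusted 5% level. None of the effect size, correlation or dropout rate is in the documents. Microplastics are also one of seven primary outcome groups, and the objective in Section 2 concerns obesity-related effects, so a null result here would not by itself decide the trial. The change is worth making because it is cheap and must be made before unblinding to be credible.

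**What to change.** In Section 4, for fecal microplastics, replace the interaction as the main test with one prespecified 1-df arm contrast from the mixed model, adjusted for baseline fecal microplastics. Use Week 6, or the equal-weight mean of Weeks 3 and 6 if the sponsor expects an early, sustained effect. Report the other as supportive. Name the microplastic summary and scale to which the contrast applies, and show any power statement as a range over effect size and correlation.

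The cost is a short addition to the SAP plus the decision on the summary variable; no further samples, assays or participants are needed. The downside is that one contrast no longer describes the time course, and the mean loses power if the effect is delayed.

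### Two omics primaries are tested at a flat p < 0.05 without false-discovery control or separation of the supplement's own reads, so a nominally positive result would not by itself show a host effect.

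*Combined protocol and SAP*

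**What the plan says.** Section 3.6 lists seven primary outcomes. The second is gut microbiota composition, "Assessed by Fecal Metagenomics sequencing to analyze diversity and functional genes". The third is the blood metabolic profile, "Assessed by untargeted Blood Metabolomics to identify metabolic pathway alterations". No diversity index, taxon, gene set, metabolite or pathway is named for either.

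Section 4 gives one method for all seven: "Repeated measures ANOVA or mixed-effects models will be used to analyze changes in the primary outcome measures", with the seven listed as "MPs, microbiota, metabolomics, inflammation, biochemistry, blood routine, and InBody data" and the contrast described as "comparing the interaction between Group and Time". The only error rate is the sentence beginning "Significance level is set at", which sets 0.05. There is no multiplicity or false-discovery rule, and no statement of what makes a domain positive.

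Under Section 3.3 the active pack holds L. plantarum PD01 (10 billion CFU) plus FOS, and the placebo pack holds FOS alone. The schedule is "One pack, three times daily" for 42 days. Section 3.5 places visits at Weeks 0, 3 and 6, so no sample follows a period off product. Nothing says how reads from the supplement strain are handled.

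**The concern.** There are two separate problems.

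**Multiplicity within a domain.** Metagenomic and untargeted metabolomic assays return many features. A threshold of 0.05 per feature is a 5% error rate for each one, not for the domain. Without a stricter rule, a list of altered species, genes or metabolites is expected even if the product does nothing.

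**Product reads, microbiota primary only.** Sequencing counts DNA from ingested cells along with DNA from resident bacteria. Only one arm ingests this organism, and both post-baseline samples fall during or at the end of dosing. A Group × Time signal in L. plantarum abundance, or in genes that it carries, can therefore arise from intake alone.

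These are primary outcomes of a trial whose objective (Section 2) concerns obesity-related effects of microplastic exposure. A significant omics result would be open to being read as support for that objective when it may reflect chance or detection of the product.

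**Working it through.** **Inputs from the documents.** Significance level 0.05 and Group × Time test (Section 4); three visits (3.5); 96 participants (3.2, 4) allocated 1:1 (3.4), so 48 per arm; 10 billion CFU, read as per pack, and three packs a day (3.3).

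**Assumptions, not in the documents.** Feature counts and their correlation, daily faecal bacterial output, recovery of the strain, background carriage, read depth, cell share equal to read share, and the Shannon mean and SD.

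**1. The plan's own figure.** For m independent null tests at 0.05, P(at least one false positive) = 1 − 0.95^m. This equals the stated 0.05 only at m = 1. The sample size of 96 cannot be reproduced, because no power, effect size, SD or dropout rate is given.

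**2. Expected false positives, 0.05 × m.** 100 features give 5; 500 give 25; 1,000 give 50. Correlation between features does not change these expectations.

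**3. Chance of at least one.** With independent features, 1 − 0.95^m is 40% at m = 10, 64% at 20, 95% at 59 and 99.4% at 100. For correlated features I simulated the null case: a 2-df Group × Time test (Hotelling T² on the Week 3 and Week 6 changes), 48 per arm, 1,000 runs per row.

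| Features | Correlation | Any p < 0.05 | Any at Benjamini-Hochberg 0.05 |
|---|---|---|---|
| 1 | – | 5.3% | 5.3% |
| 100 | 0 | 99.2% | 5.1% |
| 100 | 0.3, common | 94.5% | 4.8% |
| 100 | 0.5, common | 78.8% | 4.7% |
| 100 | 0.8, common | 40.0% | 2.5% |
| 500 | 0.5, common | 97.7% | 3.2% |
| 500 | 0.8, common | 53.4% | 2.2% |
| 500 | 0.8, in blocks of 10 | 100% | 2.8% |

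**4. Size of the product signal.** Daily intake is 3 × 10^10 = 3e10 CFU. Share of the stool community = 3e10·r / (F + 3e10·r), with r the recovery and F the faecal bacteria per day.

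- F = 1e13 to 2e13: 0.30% to 0.15% at full recovery, 0.03% to 0.015% at 10% recovery.
- F = 5e12 to 4e13: 0.6% to 0.07% at full recovery, 0.006% to 0.0007% at 1% recovery.
- At 10 million reads, 0.015% to 0.30% is 1,500 to 30,000 reads.
- If 10 billion CFU were a daily total, the shares would fall to about one third.

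**5. Would the strain separate the arms?** If it is detected in 90% of active samples and in 10% to 50% of placebo samples, power at 48 per arm is at least 99.5%. At 70% against 50% it is 52%.

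**6. Would diversity move?** Adding a taxon at share p changes Shannon H to (1 − p)H + h(p), where h(p) = −[p ln p + (1 − p) ln(1 − p)]. With p = 0.003 and H = 3.5, the change is −0.0105 + 0.0204 = 0.0099. With an SD of 0.5 that is 0.02 SD. Power in that direction is 3.1%, against 0.05/2 = 2.5% from chance alone.

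**7. Would other taxa appear to fall?** At p = 0.003 every other taxon is multiplied by 1 − 0.003 = 0.997, which is negligible at this sample size.

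**The case against.** A reader might infer that these two primaries will come out positive whatever PD01 does. The documents do not support that. It would require feature-by-feature testing together with a rule that any significant feature makes the domain positive. Section 4 states neither. A single diversity index, which Section 3.6 permits, would carry a 5% false-positive rate, and under strong common correlation the any-feature rate is 40% to 53%. What stands is that the plan excludes neither practice, and its wording for both outcomes points to testing many features.

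The product-read argument is also narrow. It has no bearing on blood metabolomics, it does not materially move diversity, and the displacement of other taxa is negligible at the shares computed. A reader might further assume that the strain is almost absent from placebo samples. The documents do not say so: Section 3.2 excludes recent probiotic users but does not establish background carriage, and with high carriage the arms may not separate clearly. The strain-level signal therefore may arise; it is not certain.

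Finally, the strain difference is real, so it is not a false positive in the usual sense. That is correct, and it is why false-discovery control cannot deal with it. The issue is interpretation: the difference shows intake, not a host effect.

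**Conclusion.** The concern holds in two distinct parts. First, a flat 0.05 with no false-discovery control covers the metagenomic and metabolomic primaries. Feature-wise testing would then declare about 5% of null features altered, and even the most favourable many-feature scenario simulated gives a 40% chance of at least one false positive, eight times the nominal 5%. Second, for the microbiota primary only, taxon and gene abundances can differ because the active arm is taking the organism when sampled.

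A nominally positive omics primary would therefore not by itself show a host effect. The 5% per null feature follows directly from the plan; the counts and any-feature rates depend on assumed feature numbers and correlation. The size of the strain signal depends on assumed faecal load, recovery, carriage and read depth.

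**What to change.** In Section 4, before unblinding:

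1. Declare omics features significant only at Benjamini-Hochberg q < 0.05 within each family (species, gene pathways, metabolites), in place of p < 0.05.
2. Name one summary microbiota endpoint at Week 6 that decides the microbiota primary, with feature-level results as supportive. The choice of index is the sponsor's.
3. Run the taxon and functional-gene comparisons with L. plantarum reads removed, and report L. plantarum abundance separately as a measure of intake and recovery.

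This needs SAP wording and analysis code, and no new samples or visits. The cost is fewer features declared significant, and native L. plantarum is not assessed in the main microbiota test. Bonferroni gives an upper bound on the loss of sensitivity: the difference detectable with 80% power at 48 per arm rises from 0.57 SD to 0.88 SD over 100 features and to 1.00 SD over 1,000. Benjamini-Hochberg is never stricter than that.

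These changes do not settle multiplicity across the seven primary domains, where even one test per domain gives 1 − 0.95^7 = 30% if the tests are independent. That needs its own rule.

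### P-selectin is listed as a serum marker, so platelet release during clotting can add noise of unknown size to this one marker and blur its reading as inflammation

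*Combined protocol and SAP*

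**What the plan says.** Section 3.6, primary outcome 4, is a single line on inflammatory cytokines: "Measurement of serum markers including MCP-1, IL-1β, IL-6, TNF-α, P-selectin, CRP, etc". P-selectin is one of six markers named there, and the item is one of seven primary items.

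Primary outcome 6 is a blood count: "Routine blood examination: Assessed by automatic blood cell analyzer". Its named content is limited: "Includes white blood cell count (WBC) and five-part differential". Platelet count is not named.

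Section 3.5 gives the timing: "Visits occur at Baseline (Week 0), Mid-term (Week 3), and End-point (Week 6"). No section states a tube type, anticoagulant, clotting time, centrifugation rule or storage rule, and none offers plasma as an alternative for P-selectin.

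Section 4 analyses the inflammation outcome by repeated measures ANOVA or a mixed model, "comparing the interaction between Group and Time". It mentions no adjustment for sample handling or platelet count, and no log or percentage scale.

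**The concern.** Platelets store P-selectin and release it when they are activated, and clotting activates them. This is general laboratory knowledge; the documents do not discuss it. Serum is what remains after blood has clotted. A serum P-selectin value therefore adds to the circulating level, which is what the trial wants as a sign of inflammation, an amount released in the tube. That amount can vary with platelet number, clotting time and temperature, and the plan fixes none of the handling conditions.

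At stake is how well one primary marker can be read. If release is large and variable, a true change in circulating P-selectin is harder to detect, and a null result is harder to interpret. Release cannot be subtracted after the sample has clotted, so the specimen has to be chosen before sampling.

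**Working it through.** The plan gives no effect size, SD or power for any outcome, so it has no figure to reproduce. The calculation below only illustrates how the loss behaves.

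**Inputs from the documents**
- Total sample: "96 participants" (section 4).
- Allocation: "will allocate subjects 1:1 to the two groups" (section 3.4), so 96 / 2 = 48 per arm. No dropout is assumed.
- Significance level 0.05 (section 4). Two-sided is assumed, because sidedness is not stated.

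**Assumptions (not in the documents)**
- Circulating level scaled to 1, with residual SD 0.25 (CV 25%).
- True fall of 20%, an absolute difference of 0.20.
- Release makes up a share s of the serum value, with s = 50% or 80%.
- Release is additive, independent of the circulating level and equally distributed in both arms, with a CV of 0, 10% or 25%.

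**Formulas**
- Mean release m = s / (1 − s): 1 at 50% and 4 at 80%.
- SD of the serum value = √(0.25² + (m × release CV)²).
- SE of the arm difference = SD × √(2/48) = SD × 0.2041.
- z = 0.20 / SE, and power ≈ Φ(z − 1.96). The opposite tail adds at most 0.2 percentage points.

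**Results**

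| Release share | Release CV | Release SD | Total SD | SE | z | Power |
|---|---|---|---|---|---|---|
| 50% | 0 | 0 | 0.250 | 0.051 | 3.92 | 97.5% |
| 50% | 10% | 0.10 | 0.269 | 0.055 | 3.64 | 95% |
| 50% | 25% | 0.25 | 0.354 | 0.072 | 2.77 | 79% |
| 80% | 0 | 0 | 0.250 | 0.051 | 3.92 | 97.5% |
| 80% | 10% | 0.40 | 0.472 | 0.096 | 2.08 | 55% |
| 80% | 25% | 1.00 | 1.031 | 0.210 | 0.95 | 16% |

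**What the table shows.** A constant release costs no power: it raises both arms equally and leaves the absolute difference at 0.20. Only the percentage difference shrinks, to 0.20/2 = 10% at 50% release and 0.20/5 = 4% at 80%. Power is lost through the SD of the release, which is its mean times its CV. The same release CV therefore does far more damage at 80% than at 50%.

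**Check with a different model.** Suppose only a fraction R of the serum variance is in-vivo signal, so that the standardised difference shrinks by √R. With 48 per arm, the standardised difference detectable at 80% power is (1.96 + 0.84) × √(2/48) = 0.57. At that true difference, power is 80%, 71%, 51% and 34% for R = 1, 0.8, 0.5 and 0.3. The direction is the same, and R is again an assumption.

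**The case against.** The strongest case on the other side has four parts.

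1. **The documents give no magnitude.** A reader might infer that serum P-selectin mostly reflects tube handling and platelet count, and that a null result would say nothing. That needs a release share and a release variability, and the documents contain neither. What stands is contamination of unknown degree.

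2. **A steep loss of power can be built in by assumption.** A reader might hold the CV at 25% in serum as well as in plasma and conclude that power falls to 50% at 50% release or 12% at 80%. That raises the absolute SD from 0.25 to 0.50 or 1.25. Under independent release this means a release SD of √(0.50² − 0.25²) = 0.433 or √(1.25² − 0.25²) = 1.225, that is, release CVs of 43% (0.433/1) and 31% (1.225/4). Nothing in the plan supports those values. The objection stands against that calculation. The table above still shows that large and variable release would hurt.

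3. **Randomisation and blinding protect the comparison.** A reader might infer that a positive result could come from tube handling. Section 3.4 allocates 1:1 and blinds investigators and participants, and there is a baseline sample, so handling noise should not differ by arm. If the product changed platelet count, that would itself be an effect of treatment, although not the circulating P-selectin effect intended. The objection stands: the documents give no ground for claiming bias.

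4. **The scope is small and the wording thin.** P-selectin is one of six named markers in one of seven primary items, with no separate test or decision role. The word serum in a one-line list may be loose usage, and a laboratory manual could govern specimens. The point on scope stands. On wording, no manual is cited, and the plan followed as written gives serum.

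**Conclusion.** The concern holds in a limited form. As written, the plan measures P-selectin in serum with no handling rule, which can add non-differential noise and make this one marker harder to interpret as inflammation. The arm comparison is not biased, provided handling does not differ by arm, and the point does not extend to the other markers in primary outcome 4.

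The size of the loss is unknown. Under the stated assumptions it ranges from none (constant release) to a fall from 97.5% to 16% power (80% release share, release CV 25%). The release share and its CV, the circulating CV of 25% and the 20% fall are all assumed. The calculation is also a simple two-arm comparison. If a participant's release is stable across visits, the baseline sample would remove part of the noise and the loss would be smaller.

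The point merits a correction because the remedy is cheap and has to be in place before sampling. It does not threaten the validity of the trial as a whole.

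**What to change.** In section 3.6, primary outcome 4, state that P-selectin is measured in platelet-poor plasma from an anticoagulated tube taken at the same venepuncture, and centrifuged within one fixed interval that is the same at Weeks 0, 3 and 6. Leave the other markers in serum.

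If only serum is available, take P-selectin out of the primary list and report it as exploratory. Do not adjust it for post-baseline platelet count: treatment could change that count, and the plan does not list it as a recorded variable.

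The cost is one extra spin and aliquot per visit and a check that the assay kit is validated for plasma. The blood count in primary outcome 6 needs unclotted blood, so an anticoagulated tube is probably drawn already. Because the plan gives no tube types or volumes, one extra tube per visit may be needed.
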